2.7.2 Inferential Analysis for the Secondary Immunogenicity Endpoints

- An ANOVA with the fixed factors treatment group (CV1, CV2, A, B, C, D, M1, M2) will be used to compare ٠ PRNT functional antibody geometric mean titers (GMT) per visit (incl. Day -28).
- An ANOVA with the fixed factors treatment group (CV1, CV2, A, B, C, D, M1, M2) will be used to compare . ELISA functional antibody geometric mean titers (GMT) per visit (incl. Day -28).
- Seroconversion rates (SCR) will be compared between treatment groups. Seroconversion will be defined as anti-Chikungunya PRNT₅₀ titers \geq 10.
- The CHIKV PRNT50 GMT 28 days after first vaccination (i.e. Day 28 for group A and C; Day 56 for group B and D), between the four baseline (Day 0) measles titer groups, defined by baseline percentiles (0 to <25%, 25 to < 50%, 50 to <75%, 75 to 100%), will be compared by an ANOVA with fixed factors baseline measles titer group. No stratification by dose groups is intended.
- An ANOVA with the fixed factors treatment group (CV1, CV2, A, B, C, D, M1, M2) will be used to compare T-• cells (geometric mean values) per visit.

And additionally for Final Analysis:

The CHIKV PRNT₅₀ GMT 28 days after second vaccination (i.e. Day 56 for group A and C; Day 224 for group B and D), between the four baseline (Day 0) measles titer groups, defined by baseline percentiles (0 to <25%, 25 to < 50%, 50 to <75%, 75 to 100%), will be compared by an ANOVA with fixed factor baseline measles titer group. No stratification by dose groups is intended.

- An ANOVA with the fixed factors treatment group will be used to compare PRNT antibody geometric mean titers (GMT) 4 weeks after second vaccination between group A and B (i.e. comparing the GMT for A at Day 56 with the GMT of group B at Day 224).
- An ANOVA with the fixed factors treatment group will be used to compare PRNT antibody geometric mean titers (GMT) 4 weeks after second vaccination between group C and D (i.e. comparing the GMT for C at Day 56 with the GMT of group D at Day 224).
- An ANOVA with the fixed factors treatment group will be used to compare PRNT antibody geometric mean titers (GMT) 4 weeks after second MV-CHIK vaccination between group M1 and M2 (i.e. comparing the GMT for M1 at Day 56 with the GMT of group M2 at Day 224).

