### 13.4 Sample Size Justification

No formal sample size calculation has been performed for this phase 2 trial, but the sample size is typical for phase 2 trials, and in our experience, has been useful to assess the immunogenicity of vaccines.

Results of the predecessor study MV-CHIK-101 allow to assess the usefulness of the chosen sample size:

In phase I study MV-CHIK-101, a GMT of 7.3 (LOG10 SD 0.254) at day 28 in the placebo group and a GMT 13.7 (LOG10 SD 0.515) in the lowest dose group (MV-CHIK 0.05 mL = 1.5 x10^4 TCID50) was observed. Both higher dose groups (MV-CHIK 0.25 mL = 7.5 x10^4 TCID50; 1 mL = 3 x10^5 TCID50) demonstrated higher GMTs of 48 (LOG10 SD 0.466) and 45.7 (LOG10 SD 0.579).

In the present phase II study, the sample size of 60 subjects in the MV-CHIK dose group vs. 10 subjects in the corresponding control group within each dose group A-D will allow for a detection of a GMT of 15.4 (MV-CHIK) vs. 7.3 (placebo) with a LOG10 SD of 0.6 vs. 0.26 and statistical power of 80% (two-sided alpha=5%, unequal-variance t-test). Between dose groups, the sample size of 60 subjects per group will allow for a comparison of a GMT of 45.7 vs. 22.4 (LOG10 SD 0.6 for both groups) with a statistical power of 80% (two-sided alpha=5%, equal-variance t-test).

Since the magnitude of GMTs and LG10 DS in this assessment is comparable to the observed results in study MV-CHIK-101, and the statistical methodology applied in the current study has a higher statistical power than pairwise t-tests, the chosen sample size seems adequate.

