2.7 Inferential Analyses

Inferential analysis on immunogenicity endpoints will only be performed on the PP and ITT population. The significance level will be 0.05. All p-values will be two-sided and rounded to four decimal places.

GMTs and GMT ratios will be estimated by applying an analysis of variance (ANOVA) by using log-10 transformed data and taking the anti-log of the resulting point estimates for the least squares means, least squares means differences and the corresponding 2-sided 95% Cls. Pairwise comparisons for multiple comparisons will be adjusted according to Tukey-Kramer. For the definition of the baseline percentiles treatment groups A, B, C and D will be used.

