2.7.1 Inferential Analysis for the Primary Endpoint

The primary immunogenicity analysis will compare the PRNT₅₀ antibody geometric mean titer (GMT) on Day 56 between the treatment groups (CV1, CV2, A, B, C, D, M1, M2).

GMTs and GMT ratios will be estimated with including the factor vaccination group. GMTs for the MV-CHIK groups will be compared pairwise.

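### The eight-group ANOVA at each visit uses one residual variance for dosed and undosed groups, so Day 28 intervals for A, C and M1 are too short and Day 56 intervals for CV1, CV2 and M2 are about twice as wide as they should be

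*SAP*

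**What the plan says.** SAP 2.7 takes GMTs and GMT ratios from an ANOVA on log10 titres, "taking the anti-log of the resulting point estimates for the least squares means, least squares means differences and the corresponding 2-sided 95"% confidence intervals. It adds: "Pairwise comparisons for multiple comparisons will be adjusted according to Tukey-Kramer". For the primary endpoint, SAP 2.7.1 compares Day 56 titres "between the treatment groups (CV1, CV2, A, B, C, D, M1, M2"), and "GMTs and GMT ratios will be estimated with including the factor vaccination group". SAP 2.7.2 applies the same eight-level factor at every visit: "An ANOVA with the fixed factors treatment group (CV1, CV2, A, B, C, D, M1, M2) will be used to compare" PRNT titres, then ELISA titres and T-cell values. We found no Welch test, group-specific residual variance, homogeneity check or sensitivity analysis for unequal variances in either document.

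SAP 6 codes every PRNT titre below 10 as 5. Protocol 13.4 plans the vaccine-control comparison with a log10 "SD of 0.6 vs. 0.26 and statistical power of 80% (two-sided alpha=5%, unequal-variance t-test").

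SAP 2.7.2 also lists separate ANOVAs for A vs B, C vs D and M1 vs M2, four weeks after the second MV-CHIK dose.

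**The concern.** A fixed-factor ANOVA with no stated variance structure estimates one error variance from all groups. Here the groups differ by design. Those not yet given MV-CHIK have mostly sub-threshold titres, all coded 5, so their spread is small. By the schedule in SAP 1.2 and 2.3 these are CV1, CV2, B, D and M2 at Day 28 (180 of 320 subjects), CV1, CV2 and M2 at Day 56 (60 of 320), and CV1 and CV2 at Days 196 and 224 (40 of 320).

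Averaging small and large variances makes intervals too short for dosed groups and too long for undosed ones. Choosing dose and schedule for Phase 3 is a stated secondary objective, and Day 28 A vs C is the randomised comparison of one low dose with one high dose on the day-0 schedule. Because the errors run in opposite directions, a reader cannot correct for them with one rule of thumb.

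**Working it through.** **Inputs.** Group sizes (Protocol 6.3, regrouped as in SAP 2.3): CV1 20, CV2 20, A to D 60 each, M1 20, M2 20; total 320, error df 320 − 8 = 312. Log10 SDs (Protocol 13.4): planning values 0.6 (MV-CHIK) and 0.26 (control); Phase 1 Day 28 values 0.254 (control), 0.466 (medium dose) and 0.579 (high dose). No SD is given for Day 56 or later, so using 0.6 and 0.26 there is an assumption.

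**The plan's own figures first.** Protocol 13.4 gives 80% power for two cases.
- 60 vs 10, GMT 15.4 vs 7.3: difference log10(15.4/7.3) = 0.324; SE = √(0.36/60 + 0.0676/10) = 0.113; Welch df 28.6; power 79.2%.
- 60 vs 60, GMT 45.7 vs 22.4: difference 0.310; SE = 0.6 × √(2/60) = 0.110; df 118; power 80.1%.

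Both reproduce, so the inputs are read correctly.

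**Pooled SD.** MSE = Σ(n_g − 1)SD_g² / 312.
- Day 28, dosed A, C, M1 (59 + 59 + 19 = 137 df), others 175 df: (137 × 0.36 + 175 × 0.0676)/312 = 0.196; SD 0.443.
- Day 56, dosed A to D and M1 (4 × 59 + 19 = 255 df), others 57 df: (255 × 0.36 + 57 × 0.0676)/312 = 0.307; SD 0.554.

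**Intervals.** Width ratio r = pooled SD / group SD; coverage = 2Φ(1.968 r) − 1.

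| Visit | Dosed: r, coverage | Undosed: r |
|---|---|---|
| Day 28 | 0.74, 85.3% | 1.70 |
| Day 56 | 0.92, 93.1% | 2.13 |
| Days 196, 224 | 0.95, 93.8% | 2.19 |

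Simulation (100,000 trials per visit; Days 28, 56 and 224) gives dosed-group coverage of 85.0 to 85.3%, 92.9 to 93.1% and 93.6 to 93.8%. With the Phase 1 medium- and high-dose SDs, Day 28 coverage is 85.4 to 87.4%, and undosed ratios are 1.43 to 1.69 at Day 28 and 1.71 to 2.10 at Day 56.

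Example at Day 56, control group of 20 with GMT 7.3: pooled interval 4.2 to 12.8; own-SD interval (t on 19 df) 5.5 to 9.7.

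**Error rates with Tukey-Kramer.** The critical value for 8 groups and 312 df is 3.05. Per-pair error between two dosed groups is 2Φ(−3.05 r). For A vs C at Day 28 this is about 2.4%, against a nominal 2Φ(−3.05) = 0.23%; at Day 56 it is about 0.5%. Simulated familywise error over all pairs is about 7.7% at Day 28 and 4.1% at Day 56.

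**Vaccine vs control at Day 56, unadjusted, 60 vs 20, GMT 15.4 vs 7.3.** True SE = √(0.36/60 + 0.0676/20) = 0.097, Welch power 91%. Pooled SE = 0.554 × √(1/60 + 1/20) = 0.143, which is 1.48 times too large; power = Φ((0.324 − 1.968 × 0.143)/0.097) = 67%.

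**The case against.** The strongest defence has several parts.

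- **Tukey-Kramer limits false positives.** A reader might infer from 85% coverage that Day 28 dose tests run at 15% type I error. That is the unadjusted figure. The plan adjusts pairwise comparisons, and the per-pair error is then about 2.4%. Protection is lost relative to 0.23%, but the planned test does not reject 15% of the time.
- **The primary visit is little affected for dosed groups.** This stands: coverage is about 93%, and familywise error stays below 5%. The Day 56 problem is lost precision around controls, which is conservative.
- **Not every interval comes from this model.** A reader might infer that all reported GMT results are wrong. The separate A-B, C-D and M1-M2 ANOVAs after the second dose compare dosed groups and are unaffected if fitted to those pairs alone; the measles-quartile analyses use another factor. Protocol 13.1 names those three pairs for p-values, not A vs C. SAP 2.7.1 does ask for pairwise comparison of the MV-CHIK groups, which includes A vs C, but it does not list a vaccine-control test explicitly.
- **MV-CHIK group does not mean dosed.** A reader might infer that every MV-CHIK group has intervals that are too narrow. At Day 28, B, D and M2 have had no MV-CHIK, and theirs are too wide.
- **Controls are not constant on the plan's figures.** If every undosed titre were coded 5, Day 28 coverage would fall to about 81%. But a control GMT of 7.3 with SD 0.254 in Phase 1 is incompatible with all values being 5, so this is an extreme case.

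None of this removes the mechanism. The SAP does not use the term pooled variance, but nothing in it provides for anything else.

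**Conclusion.** The concern holds in a limited form. The model assumes equal variances that Protocol 13.4 does not expect, and its intervals err in both directions. The clearest understatement of uncertainty is at Day 28, a secondary time point: about 85% coverage for A, C and M1 (85 to 87% with Phase 1 medium- and high-dose SDs) and familywise error of about 7.7%. At the primary Day 56 visit the main effect is over-wide intervals for CV1, CV2 and M2, by about 2.1 times (1.7 to 2.1), and a loss of unadjusted vaccine-control power from 91% to 67% in the planning scenario. That last result runs against the statement in Protocol 13.4 that the planned method has more power than pairwise t-tests.

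These sizes rest on full planned enrolment, normal log titres, and SDs in this trial resembling the planning or Phase 1 values; at Day 56 and later that is an assumption. The change should be made, but the documents do not support calling the primary dose comparisons invalid.

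**What to change.** In SAP 2.7, specify group-specific residual variances (PROC MIXED with REPEATED / GROUP=treatment and Satterthwaite degrees of freedom) or Welch-type intervals. Replace pooled-variance Tukey-Kramer with an adjustment valid under unequal variances, such as Games-Howell; changing the variance model alone would leave the planned multiplicity control without a valid basis. Where all or nearly all titres in a group are below 10, report seropositivity with an exact confidence interval and leave the group out of the variance model, because its variance cannot be estimated sensibly. State that the A-B, C-D and M1-M2 models are fitted to those pairs only.

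With own-SD intervals, simulated coverage is about 95% in every group at Days 28, 56 and 224. The price is wider intervals for dosed groups: at Day 28 the limits for A or C move from the GMT multiplied and divided by about 1.30 to about 1.43, while those for CV1 or CV2 tighten from about 1.57 to 1.32. No new data are needed. The work is a small SAP and programming change, but since Protocol 13.1 also specifies the ANOVA with Tukey-Kramer, it should be recorded in SAP 2.17 as a change to the planned analysis. The preliminary analysis was scheduled for August 2017, before this SAP version of May 2018, so the change would apply to the final analysis.

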### 3.2 Secondary Objectives

- To investigate the immunogenicity, safety and tolerability of MV-CHIK booster dose 24 weeks after primary immunization
- To investigate the immunogenicity, safety and tolerability of MV-CHIK during the treatment period up to 28 days after the last treatment
- To identify dose and schedule of MV-CHIK to forward to Phase 3 clinical development

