## **6.2 Discussion of design**

The double-blind design will allow the most objective scoring of any adverse events. Block-randomization is considered to be necessary because of the limited group sizes.

Priorix® will be used as a control-vaccine because MV is the backbone of MV-CHIK. In case of unavailability or shortness of supplies also MMR-Vax-Pro or an equal measles vaccine may be used as control-vaccine.

Saline, serving as placebo control will be used to allow the assessment of absolute differences in signs and symptoms induced by MV-CHIK on an individual level and in order to maintain blinding of the sequence.

The sequence of vaccine injection on days 0 and 28 will allow assessment of the immunogenicity of two shots of the MV-CHIK vaccine 4 weeks apart. This sequence would be more realistic, if MV-CHIK will be used as a traveler vaccine.

The sequence of vaccine injection on days 28 and 196 will provide information on the immunogenicity of MV-CHIK after a single shot up to 196 days, which is also relevant for travelers. It will also allow testing of the immunogenicity of two shots of MV-CHIK (boosting vaccination after 24 weeks) in case the interval of 28 days between vaccinations is suboptimal for immunogenicity.

The shedding of infectious measles virus particles from a subset of immunized study subjects will be determined. Samples for shedding will only be collected from a subset of study subjects (of treatment groups A-D) that are enrolled at the study site in AKH Vienna. Body fluids including saliva, urine and whole blood will be collected at Visits 1, 2, and 5. In addition, the subjects will be asked to return to the study site on days 7, 10 and 14 after the first immunization for collection of saliva, urine and whole blood.

The induction of Chikungunya virus specific T cells is a critical step in the generation of a functional immune response. Only subjects (of all treatment groups) that are enrolled at study sites in Vienna will be included in a T cell investigation. For this purpose, peripheral blood monocyte cells (PBMC) from whole blood will be collected from the subjects. The frequency of Chikungunya virus specific T cells will be analyzed in vitro.

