### 6.3 Randomization

At Visit 0, eligible subjects will be assigned to one of six treatment groups in timely order and receive a three-digit randomization number using randomization envelopes provided by data management. The site will also be provided with emergency envelopes for unblinding in case of emergency and if knowledge of the treatment assignment is mandatory for emergency treatment.

Treatment groups A, B, C and D:

All subjects will receive three i.m. injections on study day 0, 28 and 196. Subjects randomly allocated to group A or B will receive either MV-CHIK low dose or a control-vaccine (Priorix® or MMR-Vax-Pro® or equal measles vaccine). Subjects randomly allocated to group C or D will receive MV-CHIK high dose or a control-vaccine. Block randomization will be used with a randomization ratio of 1:6 (control-vaccine : MV-CHIK).

All subjects of treatment groups A, B, C and D additionally will be randomized to one of two treatment sequences. Group A + C will receive vaccinations (MV-CHIK or control vaccine) on day 0 and 28 and placebo injection on day 196 whereas groups B + D receive placebo injection on day 0 and vaccinations (MV-CHIK or control vaccine) on day 28 and 196.

Measles booster group M1 and M2:

All subjects will receive five i.m. injections and the first injection on day -28 will be the control vaccine (Priorix® or MMR-Vax-Pro® or an equal measles vaccine). Subjects will be randomly allocated to receive MV-CHIK on day 0 and on 28 (and placebo on day 168 and 196), or to receive MV-CHIK on day 168 and on 196 (and placebo on day 0 and 28). Randomization ratio between the two booster groups will be M1 : M2 = 1 : 1

Randomization of 320 subjects to one of the six treatment groups:

Group A: MV-CHIK low : control-vaccine = 60 : 10

Group B: MV-CHIK low : control-vaccine = 60 : 10

Group C: MV-CHIK high : control-vaccine = 60 : 10

Group D: MV-CHIK high : control-vaccine = 60 : 10

Group M1:M2 MV-CHIK high day 0+28 : MV-CHIK high day 168+196 = 20 : 20

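### Low and high dose after one injection are compared per visit only (60 vs 60, twice), leaving unused the 120 vs 120 comparison that the staggered start provides

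*SAP*

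**What the plan says.** **Design.** Protocol 1.1 and 6.1 give A and B the low dose and C and D the high dose. A and C are vaccinated on Days 0 and 28. B and D receive saline on Day 0 and vaccine on Days 28 and 196. Protocol 10.1 has PRNT50 measured in all four groups on Days 28 and 56.

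**Comparisons by visit.** SAP 2.7.1 compares the treatment groups at Day 56 (primary endpoint). SAP 2.7.2 then compares "PRNT functional antibody geometric mean titers (GMT) per visit (incl. Day -28" in an ANOVA whose only factor is treatment group.

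**Comparisons by time since vaccination.** SAP 2.7.2 has two kinds:
- The measles-titer analysis takes the CHIKV titer "28 days after first vaccination (i.e. Day 28 for group A and C; Day 56 for group B and D", with a matching analysis after the second vaccination. Both ignore dose.
- Four weeks after the second dose, A is set against B, C against D and M1 against M2. These compare schedules, not doses.

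No model has dose as a factor, and no table in SAP 10.1 sets A and B together against C and D. Protocol 13.1 names the pairs A-B, C-D and M1-M2, with no low-high pair.

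**Purpose.** A secondary objective (Protocol 3.2) is "To identify dose and schedule of MV-CHIK to forward to Phase 3 clinical development". Protocol 6.2 says that the Day 28/196 sequence informs on immunogenicity "after a single shot up to 196 days, which is also relevant for travelers".

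**The concern.** The trial has to inform both the dose and the number of injections for Phase 3. For the single injection, the comparison of low with high is randomised in two cohorts that differ only in starting 28 days apart. The plan reads each cohort by itself, at a different visit: one within the primary Day 56 analysis, the other within a secondary per-visit analysis.

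Two half-size estimates of one quantity have wider limits than they need, and one can reach significance while the other does not. The SAP does not say how the two would then be weighed. It already selects the right visit for each group in the measles-titer analysis, so a combined estimate needs no new samples, visits or assays.

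**Working it through.** **Inputs**
- Group sizes, Protocol 6.3: "Group A: MV-CHIK low : control-vaccine = 60 : 10" and "Group D: MV-CHIK high : control-vaccine = 60 : 10"; B and C have the same split. Low dose: A + B = 60 + 60 = 120. High dose: C + D = 60 + 60 = 120.
- M1 and M2 are left out. They are measles-boosted, and SAP 1.2 gives them different doses in Austria and Germany.
- Between-dose planning values, Protocol 13.4: GMT 45.7 vs 22.4, log10 SD 0.6 in both groups, 60 per group, two-sided 5%, equal-variance t-test, power 80%.
- Dropout: no rate is given. Assumed 0%, with 10% as a sensitivity case.

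**Step 1: the plan's own figure.** δ = log10(45.7/22.4) = 0.3097, a ratio of 2.04. SE = 0.6 × √(2/60) = 0.1095. Noncentrality = 0.3097/0.1095 = 2.83 on 118 df. The noncentral t gives power 80.1%. The stated 80% is reproduced.

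**Step 2: both cohorts together.** SE = 0.6 × √(2/120) = 0.0775. Noncentrality = 0.3097/0.0775 = 4.00 on 238 df. Power is 97.8%. Keeping schedule in the model costs one degree of freedom, which is negligible here.

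**Step 3: side by side** (SD 0.6, no dropout, unadjusted). The CI factor is 10^(t × SE): 10^(1.980 × 0.1095) and 10^(1.970 × 0.0775).

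| | 60 vs 60 | 120 vs 120 |
|---|---|---|
| Power at ratio 2.04 | 80% | 98% |
| Power at ratio 1.65 | 50% | 80% |
| Power at ratio 1.5 | 36% | 62% |
| Ratio detectable with 80% power | 2.04 | 1.65 |
| 95% CI factor on the ratio | ×/÷1.65 | ×/÷1.42 |

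**Step 4: sensitivity.** For SD from 0.466 (the smallest Phase 1 value for the two higher doses in Protocol 13.4) to 0.6, the ratio detectable with 80% power is 1.74 to 2.04 at 60 per dose and 1.48 to 1.65 at 120. With 10% loss (54 and 108 per dose, SD 0.6), power at ratio 2.04 is 75.7% and 96.5%.

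**Step 5: two separate readings.** If each 60 vs 60 test has power 0.801, both are significant with probability 0.801² = 0.64. Exactly one is significant with probability 2 × 0.801 × 0.199 = 0.32. A split result would be common even with the same true ratio in both cohorts.

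**Step 6: the planned adjustment.** SAP 2.7 applies Tukey-Kramer to the pairwise comparisons. The size of the family is not fully clear, so both readings are shown:
- 8 groups: 320 − 8 = 312 df, critical value 3.05, power for one 60 vs 60 dose pair at ratio 2.04 about 41%.
- 6 MV-CHIK groups: 280 − 6 = 274 df, critical value 2.87, power about 48%.

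**Step 7: how sharp a dose-by-schedule check is.** SE of the difference between the two log ratios = 0.6 × √(4/60) = 0.155. The 95% CI factor on the ratio of ratios is 10^(1.97 × 0.155) = ×/÷2.02. The check can show only a large difference between schedules, so both schedule-specific ratios should be reported beside it.

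**Single-shot follow-up.** B and D are dosed on Day 28 and boosted on Day 196: 196 − 28 = 168 days, which matches the 24 weeks in Protocol 3.2.

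**The case against.** The strongest reply is that the question is already answered as designed. B vs D at Day 56 is a concurrent, randomised single-dose comparison inside the primary analysis, and A vs C at Day 28 repeats it in separate subjects. Protocol 13.4 considers the between-dose comparison at exactly 60 per group, in a Phase 2 trial without a formal sample size calculation. Both ratios will be reported and could be combined afterwards.

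Much of this stands. A reader might infer that the trial misses its stated power for dose, but the 80% is for an unadjusted 60 vs 60 test and it reproduces. The 41–48% in Step 6 belongs to the adjusted pairs, for which the protocol states no power. The per-visit ANOVA also draws its residual variance from all groups, so the halving affects the dose means and not the error degrees of freedom.

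Three other strong readings fail:
- That the SAP works by study day only. SAP 2.7.2 aligns on time since vaccination for the measles-titer and schedule comparisons.
- That the design was built to test a single shot for travellers. Protocol 6.2 calls the two-shot Day 0/28 sequence the more realistic one for travellers and the single shot only an additional interest.
- That pooling has no downside. A schedule main effect absorbs a shift in level, but not a dose ratio that differs between schedules.

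What the reply does not remove is that combining the two ratios after seeing them is not a planned analysis, and that the plan does not say which one informs dose selection.

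**Conclusion.** The point holds as an inexpensive gain in precision for a stated objective. The SAP compares low and high dose after one injection only visit by visit, although the design provides 120 vs 120. At SD 0.6, without dropout or adjustment, using all of it lowers the ratio detectable with 80% power from 2.04 to 1.65, raises power at ratio 2.04 from 80% to 98%, and narrows the CI factor from ×/÷1.65 to ×/÷1.42. The gain assumes a similar dose ratio in the two schedules. That is plausible because they differ by a 28-day shift in start, but the trial can check it only coarsely. No planned analysis is invalid as it stands.

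A reader might take the 196-day phrase in Protocol 6.2 as a further flaw in the analysis. It changes no analysis: the phrase can be read as study Day 196, and the same section gives the boost interval as 24 weeks. It is a wording matter only.

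**What to change.** Add one supportive analysis to SAP 2.7.2, and a matching table to SAP 10.1, in the same populations as the other immunogenicity tables:
- Model log10 PRNT50 28 days after the first MV-CHIK dose (A and C at Day 28, B and D at Day 56), with dose and schedule as factors.
- Report the low/high GMT ratio with its 95% CI as a single contrast outside the Tukey-Kramer family.
- Beside it, report a dose-by-schedule check and the two schedule-specific ratios (A vs C, B vs D).
- Compare seroconversion rates between doses in the same way, accounting for schedule.

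The cost is one more analysis on data that the SAP already aligns, and reliance on a similar dose ratio in the two schedules. SAP 2.2.1 places the preliminary analysis in August 2017, and the current SAP (Final 3.0) is dated 09-May-2018. If the model is added after the preliminary analysis, it should be labelled as added later and supportive.

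Separately, reword Protocol 6.2 so that single-shot follow-up reads as 168 days after the dose (Day 28 to Day 196).

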**DIAGNOSIS AND MAIN CRITERIA FOR INCLUSION:**

Healthy male or female volunteer subjects, 18 to 55 years old

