The subjects that entered the study were not pre-selected for a specifically high or low Measles antibody titer. The subjects were randomly allocated to the individual treatment cohorts. To analyze the effect of pre-existing anti-measles immunity on the immunogenicity of the MV-CHIK vaccine, we investigated if a baseline anti-measles titer would cause a difference between the PRNT50 titers on day 28 after the first immunization of all subjects in MV-CHIK dose groups (independently of their dose group). This analysis showed that subjects that had a low, medium or high measles titer at baseline were equally prone for the immunogenicity of the MV-CHIK vaccine. Thus, the pre-existing immunity to the vaccine vector did not interfere with the vaccine immunogenicity.

[figure not shown]

Figure 2: Induction of neutralizing antibodies after two immunizations – 1 month interval (Upper panel), 3 month interval (Lower panel). The data are depicted as 50% plaque reduction neutralization titers (PRNT50) for the individual subjects and Geometric Mean titers (GMT) for the cohorts on day 0, 28 and 56 (upper panel) or day 120 (lower panel). The cohorts were divided in three dose groups: low ( $1.5 \times 10^4$  TCID50/mL) medium ( $7.5 \times 10^4$  TCID50/mL) and high ( $3 \times 10^5$  TCID50/mL); the control group received Priorix, a commercially available Measles, mumps rubella vaccine. Titers <10 are referred as seronegative samples. For the purpose of display in the graph and for calculation of a GMT the negative values were depicted as 5.

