2.8 Center and Country Effect

This study is a multicentre study and conducted in three Austrian and one German site.

As the M1 an M2 dose is different in both countries (cp. Section 1.2) a stratification by countries will be prepared only for listings. No stratification by centers inside the country will be done.

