4.1 Demographic Aspects

The following tables / listing will be provided:

- Age (calculated as difference in years between year of birth and year of informed consent) will be tabulated by treatment group and overall (summary statistics).
- Gender by treatment group and overall (frequency statistics)
- Ethnicity will be tabulated by treatment group and overall (frequency statistics)
- A data listing of all demographic data will be prepared (subject number, treatment group, date of birth, date of informed consent, age, gender and ethnicity).

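### The baseline measles-titre comparison is observational but has titre group as its only model term, and no planned output shows whether age, sex or country differ between the titre groups

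*SAP*

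**What the plan says.** The comparison is "between the four baseline (Day 0) measles titer groups, defined by baseline percentiles" (SAP 2.7.2), and the SAP states that the means "will be compared by an ANOVA with fixed factors baseline measles titer group". It is specified 28 days after the first vaccination and, for the final analysis, 28 days after the second. Stratification by dose is ruled out. On how the cuts are made, SAP 2.7 says: "For the definition of the baseline percentiles treatment groups A, B, C and D will be used".

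Possible covariates are collected but kept away from this analysis. SAP 4.1: "Age (calculated as difference in years between year of birth and year of informed consent) will be tabulated by treatment group and overall"; gender is handled the same way. SAP 2.8 says that "a stratification by countries will be prepared only for listings", and centres are not stratified. The enrolled population is broad: "Healthy male or female volunteer subjects, 18 to 55 years old" (Protocol synopsis), at sites in Austria and Germany.

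The stated purpose varies. The secondary endpoint (Protocol 4.1.2, SAP 1.3.2) speaks of a relation between PRNT50 and baseline measles titre. Protocol 13.1 speaks of assessing the effect of pre-existing immunity.

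**The concern.** Randomisation protects comparisons among groups A to D. It does not protect a comparison between groups formed from a measured baseline characteristic. If age, sex or country is related both to Day 0 measles titre and to the PRNT50 response, a one-factor ANOVA attributes that shared variation to titre. The bias can go either way: apparent interference where there is none, or real interference hidden. With no output showing age, sex or country by titre group, the reader of the results could not judge which had happened.

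Phase 1 shows how such a result is used. A comparison by baseline titre, pooled over dose and with no adjustment described, led to the statement "Thus, the pre-existing immunity to the vaccine vector did not interfere with the vaccine immunogenicity" (Protocol 2.4). The Phase 2 analysis has the same structure and is the only planned test of its endpoint.

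**Working it through.** **Inputs from the documents.** MV-CHIK subjects: "Group A: MV-CHIK low : control-vaccine = 60 : 10" (Protocol 6.3), with the same ratio in B, C and D, so 4 × 60 = 240, or 60 per quartile. Log10 SD 0.6 (Protocol 13.4). Two-sided alpha 0.05 (SAP 2.7). Age 18 to 55.

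**Assumptions not in the documents.** Age is uniform over 18 to 55 and log titre is roughly normal. The correlation between age and log titre is r, the fall in log10 PRNT50 per decade of age is b, and there is no true titre effect.

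**1. The plan's own figure.** Protocol 13.4 states 80% power for GMT 45.7 vs 22.4 with 60 per group. Difference log10(45.7/22.4) = 0.310; standard error 0.6 × √(2/60) = 0.1095; noncentrality 2.83 on 118 df; power 80.1%. It reproduces. No power or precision is stated for the titre-group analysis.

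**2. Precision of the planned comparison.** The Tukey 95% half-width between two quartiles of 60 is (3.659/√2) × 0.6 × √(2/60) = 0.283 log10, a factor of 1.92.

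**3. Bias from age alone.** The quartile means of a standard normal are ±1.271 and ±0.325, so the top and bottom quartiles differ by 2.542 SD. The SD of age is 37/√12 = 10.68 years, or 1.068 decades. The expected shift between top and bottom quartiles is therefore −b × r × 1.068 × 2.542 = −2.715 × b × r log10.

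For the F test on 3 and 236 df (critical value 2.643), the noncentrality is 60 × 3.442 × (1.068 × b × r)² / within-quartile variance, where 3.442 is the sum of the squared quartile means.

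| r | b | Shift (log10) | GMT ratio, top/bottom | Noncentrality | Rejection, planned ANOVA |
|---|---|---|---|---|---|
| 0.2 | 0.05 | −0.027 | 0.94 | 0.07 | 5.4% |
| 0.4 | 0.10 | −0.109 | 0.78 | 1.05 | 11.8% |
| 0.6 | 0.15 | −0.244 | 0.57 | 5.42 | 46.7% |

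The table takes 0.6 as the total SD. Taken as the SD around the age line, the last row gives 43.8%. Simulation (2,000 or 4,000 trials per case) gave 45% to 47% there, so about 46% is carried forward. With age in the model, simulated rejection was about 5% and the ratio about 1.00 in all three cases. With r = 0 or b = 0, both models rejected at about 5%.

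**4. Masking.** Here age and log titre are both standardised, total SD is 0.6, and the direct titre effect is −0.25 SD per SD, so the true ratio is 10^(−0.25 × 0.6 × 2.542) = 0.42. Age acts in the opposite direction.

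| r | Age effect (SD per SD) | Power, planned ANOVA | Power with age in model |
|---|---|---|---|
| 0 | 0.3 | 0.89 | 0.92 |
| 0.3 | 0.3 | 0.46 | 0.85 |
| 0.5 | 0.3 | 0.19 | 0.73 |
| 0.5 | 0.5 | 0.05 (observed ratio 1.00) | 0.81 |

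**5. Weak links.** On this standardised scale with no true titre effect, age-titre and age-response correlations of 0.1 to 0.2 each give rejection of only 0.051 to 0.070.

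**6. Dose.** Dose is randomised within A to D, so omitting it does not confound in expectation. It adds noise: if the doses differ by 0.310 log10, the SD rises from 0.60 to √(0.36 + 0.155²) = 0.62.

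No calculation was made for sex or country. They rest on the same logic, without a size.

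**The case against.** The strongest reply is that nothing in the documents links age, sex or country to measles titre or to PRNT50. A reader might infer that titre is known to follow birth year and that the analysis is therefore biased. The documents do not support that. Phase 1 reported no difference by baseline titre and says nothing about age. This stands: the point is a risk of unknown size.

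The larger figures also need strong effects. A fall of 0.10 log10 per decade over 3.7 decades is 0.37 log10 (2.3-fold), more than the 0.310 dose contrast used in Protocol 13.4, and still moves rejection only to about 12%. The 46% case needs 0.555 log10 (3.6-fold) and a correlation of 0.6. This stands too.

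A reader might also call the titre groups self-selected. They are not; they are cut at percentiles of a measured titre.

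Nor is this the only evidence on vector immunity, since M1 and M2 address it by design. That limits the importance without removing the point. The relation to baseline titre is an endpoint of its own. M1 and M2 have 20 subjects each, and their tables pool low dose (Austria) with high dose (Germany) (SAP 2.3).

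Finally, an unadjusted comparison does describe a relation, and adjustment is not automatically right. The measles ELISA values are truncated at 50 and 5000 (SAP 6) and capture antibody only. If age carries vector immunity that the assay misses, adjusting for age could remove real interference. This is a good reason to keep the planned result and not replace it.

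**Conclusion.** The point holds in a limited form. The comparison is observational, the model has one factor, and no planned output lets a reader check the titre groups for imbalance in age, sex or country. Protocol 13.1's wording of an effect goes further than this design supports.

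With no true vector effect and under the assumptions shown, the bias ranges from negligible (ratio 0.94, rejection about 5%) to serious (0.57, about 46%). It is nil if age is unrelated to either titre or response. At the upper end the shift of 0.244 log10 is close to the comparison's own half-width of 0.283. In the masking direction, power for a true ratio of 0.42 could fall from 0.89 to as low as 0.05.

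The documents do not show where the trial lies in these ranges, and they do not establish that the result will be wrong. Severity is modest. The case for acting is that the covariates are already recorded and an adjustment chosen after seeing the data would be less credible.

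**What to change.** In SAP 2.7.2:

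- Keep the one-factor ANOVA as planned.
- Beside it, pre-specify a model of log10 PRNT50 on baseline titre group with age (continuous), sex and country, plus the randomised dose and schedule, for the analysis 28 days after the second vaccination. Report adjusted GMTs and ratios.
- Apply the same model to the first-vaccination analysis, labelled post hoc where its preliminary run has already taken place. SAP 10.1 marks those tables (3.1.10 and 3.1.11) for the preliminary analysis only. That analysis was scheduled for August 2017, while this SAP version is dated 09-May-2018.
- Add one table of age, sex and country by titre quartile.
- Describe the result as an association, and align Protocol 13.1's wording with the endpoint.

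Cost: SAP text, one extra model per time point and one table, with no new data. As main effects the five added terms take the error df from 236 to 231 at the planned size. The model assumes a roughly linear age effect and may over-adjust if age carries vector immunity that the ELISA does not measure. Showing both models makes that visible.
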